5.5 Premature Trial Termination

Both the investigator (with regard to his/her participation) and the sponsor reserve the right to terminate the trial at any time. Should this become necessary, the procedures will be agreed upon after consultation between the two parties. In terminating the trial, the sponsor and the investigator will ensure that adequate consideration is given to the protection of the best interests of the subjects. Regulatory authorities and EC will be informed.

In addition, the sponsor reserves the right to terminate the participation of individual trial sites.

Intensive Drug Monitoring Protocol Version: 1.0

Date: 11-May-2020

Conditions that may warrant termination include, but are not limited to, insufficient adherence to protocol requirements and failure to enter patients at an acceptable rate.

Ferring Pharmaceuticals (Asia) Co., Ltd.

5.6 Study Plan

Data collection overview:

Frequency	Inclusion	Every 3 months during total 12 months
Visit Window	The Baseline Visit	The 2nd Visit to the 4th Visit
Obtaining informed consent	X	
Inclusion/Exclusion criteria	X	
Demographic information ¹	X	
Medical history ²	X	
Disease characteristics ³	X	
FIRMAGON® treatment ⁴	X	X
AE collecions ⁵	X	X
Disease condition ⁶	X	X

Definitions:

- 1. Including age and domicile place.
- 2. Including general medical history, surgical history, metastasis situation.
- 3. Prostate cancer: stage, the date of histology diagnosis, Gleason Score, presenting symptoms.
- 4. FIRMAGON® treatment information: initial dose and time, duration, dose adjustment (actions, times and reasons). Details need be collected for permanent withdrawal patients.
- 5. AE name (Verbatim term, SOC, PT), reporter info, event onset date, event stop date, action taken, outcome, seriousness, causality, medical history, concomitant medications.
- 6. Including the level of Serum PSA and Testosterone, and questions about disease progress or remission?

Ferring Pharmaceuticals (Asia) Co., Ltd.

6 Safety Reporting

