This study is a multi-center, single-arm, non-interventional, prospective study among Chinese patients with prostate cancer and need androgen deprivation therapy receiving treatment with FIRMAGON®. This program will provide the minimum 6 doses and maximum 12 doses of FIRMAGON® to enrolled patients during one-year follow-up. Patients who meet inclusion criteria and will or are accepting at least 6 self-financed doses treatment in hospital. Patients should return to the hospital for medical assessment every three months. The prescription of 6 (3 dose × 2 times) self-financed doses will be given by doctors after assessment, and the direct-to-patient pharmacy will distribute FIRMAGON® to eligible patients (patients should bring the prescriptions and the last FIRMAGON® boxes to get other doses). All enrolled patients will be followed up to collect safety information for one year from the 1st dose unless withdrawal of Informed Consent Form, discontinuation for 2 months, lost to follow-up, death, or termination due to other reasons, whichever comes first.

• Study sites

Data will be collected by China Primary Healthcare Foundation from patients or Health care providers (HCPs). 138 target hospitals are in the charity support list.

Patients number

2500 patients who are prescribed FIRMAGON® according to clinical practice by doctors in hospitals will be enrolled in this study.

• Main Inclusion Criterion

Patients must meet all the criteria listed below to be eligible for participation in the project.

- > Diagnosis with prostate cancer and need androgen deprivation therapy
- > Decision made to prescribe of FIRMAGON® prior to enrolment.
- Willingness and ability to provide written informed consent.
- The patients are from whom taken post-marketing drug FIRMAGON®.

• Main Exclusion Criterion

Any patient who meets the following criterion will not be qualified for the entry of this study:

- Not sign Informed Consent.
- Any patients who is unsuitable to participate in this study because of any other reasons will not be qualified to participate in this study.
- Data collection

The data below will be collected based on the current clinical practice and no additional data, diagnostic or monitoring procedures are applied to the patients.

Patient demographic information of age

Intensive Drug Monitoring Protocol Version: 1.0

Date: 11-May-2020

- Disease characteristics: PSA and Testosterone

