4.3 Patient Information and Written Informed Consent

This study is an observational study, even though patients will return to hospital and accept

monthly FIRMAGON® treatment, the staff of the charity must give the patient oral and

written information about the study in a form that the patient can understand and obtain the

patient's written consent before collection of identifiable patient information (hereinafter

referred to as personal data). Before consenting, the patient must be left with ample time to

consider and to pose questions. Since the study is observational, the consent only concerns

the data collection The decision to treat the patient is independent of the decision to enrol the

patient in the study.

The patient must agree that Ferring personnel, their representatives or IEC or regulatory

authority personnel may require direct access to the patient's data / personal records which

were collected, processed and stored in an anonymous form.

The patient must agree that his / her data will be processed and stored in an anonymous form

for evaluation of this study and any later overviews. Data may also be transferred in anonymous

form to third parties, e.g. other companies or authorities, that may be located in other countries

with potentially different regulations for data.

The patient will receive a copy of ICF after consenting.

The patient has the right to withdraw their consent at any time without prejudice. In the

Informed Consent Form it is stated that if consent is withdrawn, any data collected before

withdrawal of consent will be kept. The original Informed Consent Forms signed and dated by

the patient and investigators must be kept in the Charity.

For details, see the Informed Consent Form.

Page 15 of 35

Intensive Drug Monitoring Protocol Version: 1.0

Date: 11-May-2020

5 Study Design and Plan

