This study is a multi-center, single-arm, non-interventional study among Chinese patients with prostate cancer needed androgen deprivation therapy receiving treatment with FIRMAGON®. 2500 patients who are prescribed FIRMAGON® according to clinical practice by doctors in hospitals will be enrolled in this study. This program will provide the minimum 6 doses and maximum 12 doses of FIRMAGON® to enrolled patients during one-year follow-up. Patients apply for enrollment in hospital, they will return to hospital every three months for medical assessment and other three doses of FIRMAGON® prescription during the study. 138 target hospitals are in the charity support list. The direct-to-patient pharmacy will distribute FIRMAGON to patients who are defined eligible by the doctor. The patient should bring the prescriptions and the last FIRMAGON® boxes to get other FIRMAGON®.

All enrollment patients will be followed up to collect safety information for one year from China Primary Healthcare Foundation from the 1st dose unless withdrawal of Informed Consent Form, dosing interrupted for 2 months or more than 2 months since last dose, lost to follow-up, death, or termination due to other reasons (defined in section 5.4), whichever comes first. Any AEs will be filled in Adverse Event Form (as Appendices), processing and submitting to relevant authorities.

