6.3 Collection and Recording of Adverse Events

The safety data will be actively collected in accordance with the follow-up time in the study plan. Patients and HCPs could report AE spontaneously after follow-up time. Collection and recording of SAEs and AEs will commence once the study participant has started first dose of

FIRMAGON®.

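### The section 5.6 schedule names no contact that closes the one-year adverse event follow-up: at 3-month spacing its last listed visit is month 9 from baseline, and early leavers have no final AE enquiry.

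*Combined protocol and SAP*

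**What the plan says.** The Study Design paragraph of the Study summary sets the safety period: "All enrolled patients will be followed up to collect safety information for one year from the 1st dose". It lists the usual early ends, and section 5 gives the same period and the same origin.

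The only contact schedule is the table in section 5.6. Its post-baseline column is headed "Every 3 months during total 12 months", and the visits in that column are "The 2nd Visit to the 4th Visit". AE collection is marked at baseline and at those visits. Section 5 gives the spacing and its link to drug supply: "they will return to hospital every three months for medical assessment and other three doses of FIRMAGON® prescription during the study".

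Section 6.3 governs AE collection: "The safety data will be actively collected in accordance with the follow-up time in the study plan". The next sentence adds: "Patients and HCPs could report AE spontaneously after follow-up time".

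For patients who stop early, section 5.4 requires the discontinuation event to be recorded in the study database. Footnote 4 of section 5.6, which defines treatment information, says: "Details need be collected for permanent withdrawal patients". Neither provision asks for a final AE enquiry.

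**The concern.** Prescribing looks forward: a visit at the start of each 3-month interval is enough to supply that interval. AE collection looks back: it needs a contact at the end of each interval. The listed visits fit the first purpose and leave the last interval of the second open. The same holds for a patient who leaves between visits.

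Section 5.2 names AE collection as the main purpose of the programme, and section 6.1.1 asks for every AE after the first dose. Under sections 8.1 and 8.2 results are percentages of patients in the full analysis set, with no imputation, so an event that nobody asked about and nobody reported counts as no event. A reader of the report would probably take a one-year AE frequency as actively collected throughout, and could not tell from the plan whether it was.

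**Working it through.** **Inputs.** Follow-up of 12 months from first dose (Study summary; section 5). Spacing of 3 months and four contacts in all, baseline plus visits 2 to 4 (section 5.6). Three doses prescribed per visit and a maximum of 12 doses (section 5). 2500 patients (section 5). The time from first dose to baseline is not given. The Study summary admits patients who will start or are already receiving self-financed doses, so this offset can be zero or positive.

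**1. Reproduce the visit count.** 12 / 3 = 4 intervals. One contact at the start of each gives four contacts, at months 0, 3, 6 and 9 from baseline, which matches the table. It also matches the supply: 4 visits x 3 doses = 12 doses. The month numbers are inferred; the table prints none.

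**2. Try the alternatives.** Contacts at both ends of the 12 months need 12 / 3 + 1 = 5 visits (months 0, 3, 6, 9, 12), and the table has four. Four visits reach month 12 only at 4-month spacing (0, 4, 8, 12), which contradicts the stated 3 months. If a month-12 contact was intended, the header and the visit count disagree.

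**3. Length of the tail for a patient who completes the year.** Visit 4 falls at offset + 9 months from first dose, so the tail is 12 - (offset + 9) = 3 - offset months, with a floor of 0. If all 2500 patients had the same offset and completed:

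| Offset (months, assumed) | Tail (months) | Patient-years, 2500 x tail / 12 |
|---|---|---|
| 0 | 3 | 625 |
| 1 | 2 | 417 |
| 2 | 1 | 208 |
| 3 | 0 | 0 |

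The upper end is 625 / 2500 = 25% of follow-up time. Beyond an offset of 3 months the tail is 0 only if the first visit at or after month 12 from first dose is still held. With an offset of 6, for example, visit 3 falls at month 12 and visit 4 at month 15, and the plan does not say what happens to such visits.

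**4. Early leavers.** Assume an offset of 0, the last of six monthly doses at month 5, and removal two months later at month 7. The last visit is month 6, so the tail is 1 month. If a share f of patients leaves this way, the tail is 2500(1 - f) x 3/12 + 2500f x 1/12 patient-years out of 2500(1 - f) + 2500f x 7/12:
- f = 0: 625 / 2500 = 25%
- f = 0.5: 417 / 1979 = 21%
- f = 1: 208 / 1458 = 14%

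**5. The two readings of section 6.3.** If the follow-up time in the study plan means the listed visits, events after the last one rest on spontaneous reports. If it means the whole year, active collection is due to month 12 but no listed contact performs it. Either way the closing enquiry is missing from the schedule.

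**The case against.** The strongest reply is that the second reading of section 6.3 is the natural one: follow-up is a year wherever it is defined, the table header says 12 months, and spontaneous reporting starts only afterwards. On this view the visit count is a drafting slip. Collection is also not confined to table visits. The charity gathers safety information for the year from patients or health care providers, and section 4.3 says of treatment, "even though patients will return to hospital and accept" it monthly. The tail may be 0 for patients already on treatment at enrolment. The study is descriptive, with no formal hypothesis.

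Much of this stands. The full-year reading is open, so it would be wrong to say the plan commits to spontaneous reporting alone after visit 4. But that reading still leaves no named contact, and no AE enquiry is attached to the monthly treatment returns.

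Stronger inferences are tempting, and the documents do not support them:
- **A quarter of AEs would be missed.** The 25% is a share of follow-up time at the most adverse offset, not of events, and spontaneous reporting stays open. Section 1.3 says AEs came mainly early in the Chinese trial, although that sentence sits in a paragraph on injection site reactions and may not apply to all AEs.
- **Early leavers go undocumented.** Section 5.4 requires their exit to be recorded, including exits for an intolerable reaction or death, and footnote 4 adds treatment details. What they lack is a final AE enquiry.
- **Follow-up has no stated origin.** It has one, the first dose. Only the origin of the visits is unstated.

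**Conclusion.** The point holds in bounded form and should be fixed. A site that followed the section 5.6 table exactly would make no scheduled AE enquiry for up to the last 3 months of a patient enrolled at first dose, and none at exit for a patient who leaves between visits. The upper bound of 625 patient-years assumes that visits fall at months 0, 3, 6 and 9, that baseline coincides with first dose, and that everyone completes the year. It shrinks to 0 at an offset of 3 months. The real figure lies in between and cannot be located without the distribution of offsets.

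Any bias in the AE percentages would be downward and would fall most on late-onset events. Its size depends on event timing and on how completely late events are reported spontaneously, and the documents give neither. The planned sample size is not affected.

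**What to change.** In section 5.6, reconcile the 12-month header with the number of visits, give each visit's month and its time origin (first dose or enrolment), and say what happens to visits that fall after month 12 from first dose.

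Add one closing AE enquiry, by telephone call from the charity or by a check of health care provider records. It would fall at 12 months from first dose or at earlier exit, unless a scheduled visit already falls there. Make no contact after consent is withdrawn, and use provider records after a death. For every patient, record the date on which AEs were last asked about. Refer to this enquiry in section 6.3.

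The Study summary says that nothing beyond current practice is collected or monitored, so the amendment should explain that the enquiry completes the year of AE collection already promised, from sources already named, with no new tests.

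If no closing enquiry is added, state the actively solicited window in the Study summary, section 5 and the report. Present AE frequencies for that window, with later spontaneous reports shown separately.

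The cost is a short amendment submitted to the ethics committee and about one call or record check per patient. Follow-up is not lengthened. The fallback costs a shorter stated window.

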6.1 Definitions

6.1.1 Adverse Event

An adverse event (AE) is any untoward medical occurrence in a patient administered a medicinal product and which does not necessarily have to have a causal relationship with this treatment. An AE can therefore be any untoward and unintended sign (including an abnormal laboratory finding), symptom, a new disease or worsening in severity or frequency of a concomitant disease, temporally associated with the use of a medicinal product, whether or not the event is considered causally related to the use of the product. In this study, all AEs (including Serious Adverse Events) after first dose of FIRMAGON® should be collected.

Abnormal laboratory values or outcome of an examination considered as clinically significant by HCP should be reported as an AE.

6.1.2 Serious Adverse Events

A Serious Adverse Event (SAE) is any untoward medical occurrence that at any dose:

- Results in death
- Is life-threatening (NOTE: The term "life-threatening" in the definition of "serious" refers to an event/reaction in which the patient was at risk of death at the time of the event/reaction; it does not refer to an event/ reaction which hypothetically might have caused death if it were more severe)
- Requires inpatient hospitalization or results in prolongation of existing hospitalization
- Results in persistent or significant disability/incapacity
- Is a congenital anomaly/birth defect
- Is a medically important event or reaction

Medical and scientific judgment should be exercised in deciding whether other situations should be considered serious such as important medical events that might not be immediately life-threatening or result in death or hospitalisation but might jeopardise the patient or might require intervention to prevent one of the other outcomes listed in the

Ferring Pharmaceuticals (Asia) Co., Ltd.

definition above. Examples of such events are intensive treatment in an emergency room or

at home for hypersensitivity, anaphylactic reaction, angioedema that do not result in

hospitalization, or development of drug dependency or drug abuse.

6.1.3 Adverse Drug Reactions

An adverse drug reaction (ADR) is an AE for which there is at least a reasonable suspicion of

a causal relationship between an AE and a suspected medicinal product.

6.2 Relationship of an AE to studied drug(s)

When dealing with adverse events, data collector should make full use of known medical

knowledge and clinical experience to conduct a comprehensive analysis and evaluate the

association of adverse events with FIRMAGON®. The possibility of whether the studied

drug caused the adverse event must be classified as one of the following:

• Reasonable possibility:

There is evidence or argument to suggest a causal relationship between the studied drug and

the adverse event. The adverse event may occur as part of the pharmacological action of the

studied drug or may be unpredictable in its occurrence.

Examples:

Adverse events that are uncommon but are known to be strongly associated with exposure to

the studied drug.

Adverse events that are not commonly associated with exposure to the studied drug, but the

event occurs in association with other factors strongly suggesting causation, such as a strong

temporal association or the event recurs on rechallenge.

No reasonable possibility:

There is no reasonable evidence or argument to suggest a causal relationship between the

studied drug and the adverse event.

Examples:

Page 22 of 35

Intensive Drug Monitoring Protocol Version: 1.0

Date: 11-May-2020

Known consequences of the underlying disease or condition under investigation.

Adverse events common in the study population, which are also anticipated to occur with some frequency during the course of the study, regardless of exposure to the studied drug.

6.3 Collection and Recording of Adverse Events

The safety data will be actively collected in accordance with the follow-up time in the study plan. Patients and HCPs could report AE spontaneously after follow-up time. Collection and recording of SAEs and AEs will commence once the study participant has started first dose of

FIRMAGON®.

6.4 Reporting of Adverse Drug Reactions to Regulatory Agencies

China Primary Healthcare Foundation will send the collected safety information Form (AEs and SAEs) to CRO within 1 calendar day. CRO will translate it into English version and transfer to Ferring Global Pharmacovigilance (GPV) for case processing. Ferring is responsible for submission of ADRs to regulatory authorities in accordance with local reporting requirements. As requirement from Chinese authority, the reporting timelines are following:

Serious (Death/cluster): Immediately (death/cluster is detail explained in Data Collection

Flow section)

Serious: 15 days

Non-Serious: 30 days

Date 0 is when China Primary Healthcare Foundation becomes aware of an event arising after FIRMAGON® treatment. Events will be collected and sent to GVP within 3 calendar days for serious and 5 calendar days for non-serious. GPV will process the cases and generate CIOMS form on the condition of the event with the causality of FIRMAGON®. For serious, CIOMS form should be sent to local PV within 10 calendar days for submission and 25 calendar days for non-serious.

Data Collection Flow

For Death case:

Intensive Drug Monitoring Protocol Version: 1.0

Date: 11-May-2020

[figure not shown]
Ferring local PV will inform China regulatory authorities immediately regarding deaths considered related to Firmagon treatment. The investigation will be completed within 15 working days.

For cluster (group) case:

Ferring local PV will inform China regulatory authorities immediately regarding any cluster related cases. Meanwhile, complete the Basic Information Form of Cluster Drug Adverse Events. Then, complete the Drug Adverse Reaction/Event Form for each patient timely. Cluster of adverse drug events definition: an event which occurs in a relatively concentrated time period and area, damaging or threatening the health or life of a certain number of people during or after use of the same drug, and which requires emergency treatment. The same drug refers to a drug which is produce by the same manufacturer with the same drug name and is in the same formulation and strength. The event number should be above 2.

For other serious and non-serious case:

Version: 1.0 Date: 11-May-2020

Ferring Pharmaceuticals (Asia) Co., Ltd.

The flow is as following:

(1) Database establishment: the charity's database will be used as study database for this

study.

(2) Data entry: the delegated staff will collect data and login the system for data entry.

CRO check each information against source data. When any inconsistency is found, a

query will be sent to the charity. The data collector should correct data to ensure that

the data in the database is consistent with the source record.

(3) Procedure for safety report: each AE report will be filled in AE Form and sent to CRO

for creating safety report and translation. The CRO will send English version report

by email to Ferring GPV Case Processing via [contact]. That

reports requiring timely submission to authorities according to Chinese reporting

requirements will be delivered to CRO for further process.

(4) CRO will check the data regularly to ensure the quality of data.

7 Data Quality Control and Assurance

